2. Primary aim: To assess the acceptability, appropriateness, and feasibility of the intervention using various quantitative alongside qualitative data. Specifically, we will assess mins/wk of Ring-Fit Adventure™ played, attendance at virtual health coaching sessions, semi-structured interviews, participant retention, and intervention safety measured as number of adverse events.

Secondary aim: To calculate effect sizes for change across 12-wks. in MVPA, physical function, muscular strength, physical activity enjoyment, and self-efficacy. We hypothesize increases in MVPA, physical function, muscular strength, physical activity enjoyment, and self-efficacy.

Secondary aim: To determine energy expenditure of a session of Ring-Fit Adventure™ among adults with DS. We hypothesize energy expenditure akin to moderate physical activities.

B. Background and Significance

1. Study Significance: Down syndrome (DS) or trisomy 21 is the most common chromosomal abnormality associated with an intellectual disability (ID). The current incidence of DS is 1 in every 650 live births which is ~30% higher than in 1979, largely due to women conceiving after age 35. Additionally, life expectancy for people with DS has increased dramatically over the past 60 years due to advancements in disease knowledge, medical care, and caregiving services⁹. With this increase in DS prevalence through improved life expectancy, it is critical to address ways to support healthy living throughout their lifespan. Adults with DS have a higher prevalence of obesity¹⁰ and obesity associated health conditions including sleep apnea and type 2 diabetes¹¹ compared to adults without DS. Additionally, adults with DS face premature aging¹², higher rates and earlier onset of Alzheimer's disease (AD)¹³, functional decline, mobility restrictions, frailty, musculoskeletal problems, osteoporosis, and sleep problems when compared with typically developed adults¹⁴. These increased rates of chronic disease and functional decline are associated with reduced quality of life, and increased burden on families, care providers, and disability services. Chronic disease also contributes to absenteeism from disability employment, premature withdrawal from the workforce, and increased health care utilization¹⁵.

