F. Subject Criteria (See Vulnerable Populations appendix, if applicable): Primary care physician (PCP) clearance will be required for all participants. A form with PCP clearance will need to be signed before participation will be allowed. Inclusion criteria: 1) Young adults (18-30 yrs.) 2) Diagnosis of DS as determined by a Community Service Provider operating in our recruitment area under the auspices of a Community Developmental Disability Organization (CDDO). 3) Sufficient functional ability to understand directions, communicate preferences, wants, and needs through spoken language. 4) Living at home with a parent/guardian or in a supported living environment with a parent/caregiver who agrees to serve as a study partner. Exclusion criteria: 1) Unable to participate in MVPA. 2) Serious medical risk, e.g., cancer, recent heart attack, stroke, angioplasty as determined by their primary care provider (PCP).

1. Inclusion criteria: 1) Young adults (18-30 yrs.) 2) Diagnosis of DS as determined by a Community Service Provider operating in our recruitment area under the auspices of a

- Community Developmental Disability Organization (CDDO). 3) Sufficient functional ability to understand directions, communicate preferences, wants, and needs through spoken language. 4) Living at home with a parent/guardian or in a supported living environment with a parent/caregiver who agrees to serve as a study partner.
2. Exclusion criteria: 1) Unable to participate in MVPA. 2) Serious medical risk, e.g., cancer, recent heart attack, stroke, angioplasty as determined by their primary care provider (PCP)
 3. Withdrawal/Termination criteria: If at anytime during the intervention, the participant becomes unable to participate in exercise sessions, participation will be terminated by the investigator. If the participant asks to be withdrawn from the study, the participant will be removed.
 4. A study subject can participate in another study while participating in this research study.

E. Specific methods and techniques used throughout the study

1. Laboratory tests: Physical function will be assessed using the 6-minute walk test¹⁶, Timed Up and Go test¹⁷, and the Y-Balance Test¹⁸.
2. Leg strength will be assessed using a standard 5-repetition maximum protocol¹⁹ on a Cybex plate-loaded leg press. Hand grip strength of both the dominant and non-dominant hands will be assessed with a Jamar handgrip dynamometer (JWL Instruments, Chicago, IL)²⁰.

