3. **Daily physical activity, specifically MVPA, will be assessed using a Fitbit that will be synced to a tablet computer (iPad). Daily physical activity across the 12-week study activity will be assessed using a Fitbit Versa 3 monitor worn on the non-dominant wrist during each day of the intervention. Real-time data from the Fitbit will be transferred via Fitbit's Open API using R, thus participant burden is minimal. Immediate participant feedback via a graphic display of daily steps, minutes of sedentary time, time spent in light, moderate and vigorous PA will be available on the iPad. This data, accessible to health educators, will be used to provide motivation and feedback during the virtual coaching sessions. Participants will be reminded to wear and charge the Fitbit during the individual support/education sessions and will receive automatic reminder messages via the iPad.**

Study Procedures: 6-minute walk test (6-minutes), Timed Up and Go test (5-minutes), and the Y-Balance Test (5-minutes). Leg strength will be assessed using a standard 5-repetition maximum protocol (5-minutes) on a Cybex plate-loaded leg press. Hand grip strength of both the dominant and non-dominant hands will be assessed with a Jamar handgrip dynamometer (JWL Instruments, Chicago, IL), (5-minutes). Physical activity enjoyment will be assessed using the Physical Activity Enjoyment Scale (10-minutes). Self-efficacy will be assessed using the Self-Efficacy for Activity for Persons with Intellectual Disabilities Scale (10-minutes). Energy expenditure of a ring-fit session will be assessed in a volunteer sample of both patient and caregiver using a previously validated portable, open-circuit indirect calorimeter (Cosmed, Italy) which measures breath-by-breath ventilation, expired oxygen, and carbon dioxide. Study staff will schedule the assessment with participants which will involve a visit to the lab. The flow turbine will be calibrated using a 3.0-L syringe. The lightweight (~1.5 kg) portable system will be attached by a harness around the waist and shoulders of the participant

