 - e. Safety-related triggers that would cause the PI to stop or alter the study: The most likely scenario indicating the need to stop the investigation would be a failure to recruit or deliver the intervention as planned. Another issue relating to stopping rules for this trial would be new information. It is unlikely that any new information will become available during this trial that would necessitate stopping the trial
2. Data on adverse events will be reported monthly to the PI throughout this trial. We anticipate that most adverse events will be mild in nature and will allow a complete return to the same activities after a short period of time; that is, later that day or a day or two later.
3. We anticipate most adverse events (if not all) will allow a complete return to the same activities after a short period of time; that is, later that day or a day or two later. However, if a serious adverse event that prohibits participation moving forward, the participant will be terminated from the intervention.

III. Subject Participation

A. Recruitment:

1. The recruitment plan was informed by our experience with completed projects where we successfully recruited adults with DS (DK083539, HD094704, AG036909). As in our previous trials, project staff will contact local community agencies serving adults with DS, case managers, and CDDOs by mail or email, provide presentations at CDDO meetings, and text for CDDO newsletters describing the project. Interested adults with DS or their parent/caregiver will be asked to contact the study coordinator via email, our website, or a dedicated toll-free study phone number that will be included in all recruitment materials. The study coordinator will contact interested individuals by phone to answer questions and conduct an initial eligibility screen. Zoom® meetings will be scheduled with those remaining interested and potentially eligible to complete eligibility screening and to obtain informed consent or parent/guardian consent and participant assent in cases where the participant has a surrogate decision maker. We will attempt to recruit ~50% female and ≥ 30% minorities. Study staff will forward a form to the PCP requesting permission to participate.

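### Section II.I.2 reports adverse events to the PI monthly without separating serious ones, and the protocol gives no faster route for these and no method for collecting events at home

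*Combined protocol and SAP*

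**What the plan says.** Section II.I.2 gives the reporting rule for adverse events: "Data on adverse events will be reported monthly to the PI throughout this trial". Section II.I.1 makes the study team the reviewer, sets a monthly review, lists accrual and adverse event rates as the items reviewed, and names means as the analysis.

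Serious events appear once in the monitoring plan, in II.I.3: "if a serious adverse event that prohibits participation moving forward, the participant will be terminated from the intervention". The withdrawal rule under Subject Criteria (II.F.3) adds: "If at anytime during the intervention, the participant becomes unable to participate in exercise sessions, participation will be terminated by the investigator". Section II.H.2.c assigns someone to keep the sponsor and the IRB informed, without a time limit.

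Safety is also an outcome. The primary aim (I.A.2, repeated in II.A) includes "intervention safety measured as number of adverse events". The timeline places the game sessions at home and the coaching on Zoom. Coaching is described under daily physical activity: "This data, accessible to health educators, will be used to provide motivation and feedback during the virtual coaching sessions" and "Participants will be reminded to wear and charge the Fitbit during the individual support/education sessions".

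**The concern.** Two things depend on the same missing instruction.

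The first is participant safety. The risk section names blood pressure changes, heart rhythm changes and heart attack, all described as very rare. The investigator can act on such an event only after hearing of it, and the only interval stated for hearing of it is monthly. The case that matters is a participant who has a serious event, recovers enough to play, and continues before the PI knows.

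The second is the outcome itself. If nobody is told to ask about events at home, the count depends on what participants or caregivers volunteer. A low count could then mean few events or few questions. That weakens a measure on which the pilot is meant to judge feasibility.

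**Working it through.** The plan gives no event rate, reporting delay or safety threshold, so there is no figure to reproduce. The check is whether any section supplies a faster route for serious events or a way to collect events.

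1. **Reporting interval.** II.I.2 says monthly, with no split by seriousness. II.I.1 also says monthly. No other interval for adverse events is given.
2. **Serious events.** II.I.3 states a consequence, removal from the intervention. It gives no route, recipient or deadline.
3. **Authority to act.** II.F.3 names the investigator as decision-maker at any point in the intervention. This presupposes knowledge of the event but does not say how it arrives.
4. **Onward reporting.** II.H.2.c covers information going out to the sponsor and IRB. It does not cover information coming in from participants.
5. **Measures before entry.** Physician clearance ("A form with PCP clearance will need to be signed before participation will be allowed") and the exclusion for serious medical risk lower the chance of an event. Both apply before participation and neither is a reporting route.
6. **Contacts during the intervention.** A caregiver must serve as study partner, but no section gives that person a reporting duty. Coaching appears in every intervention row of the timeline, but its stated content is motivation, feedback and device reminders. Fitbit data are visible to health educators, and an activity drop might be noticed, but no section makes it a safety signal.
7. **Backstop.** Review is by the study team alone, and IV.C.2 plans no third-party monitoring. The stopping considerations in II.I.1.e are recruitment, delivery and new information, with no adverse event trigger.

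For ascertainment, it helps to see how little of the scheduled time is spent with staff in the room. Inputs are the timeline durations.

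- Weeks 1 to 12, at home or by video: 90 + 120 + 150 + (9 × 180) = 360 + 1,620 = 1,980 minutes.
- Testing visits, weeks 0 and 13: 2 × 120 = 240 minutes.
- Share away from the site: 1,980 / (1,980 + 240) = 1,980 / 2,220 = 0.89.

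The table does not say whether coaching time is inside the weekly totals, so 0.89 is the share away from the site, not the share without any staff contact. It does show that events seen in person by staff cannot be the main source of the count.

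One further fact bears on volunteered reports. Under III.F, participants keep the Fitbit, game and console only if they complete the intervention. It is an inference, not something the documents state, that this could discourage mentioning an event that might end participation.

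**The case against.** The strongest reply is that II.I.2 describes periodic aggregate surveillance. It follows a list that reviews rates, monthly, by means. On that reading it says nothing about individual serious events, and II.F.3 shows that the investigator is expected to act between reports. This is a fair reading and nothing forbids earlier contact. It still leaves serious events with no stated route.

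A second reply is that a late termination decision matters little for someone already unable to exercise. That is right. The point rests on participants who can and do continue.

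A third is that coaching contact, a caregiver partner and Fitbit data make a long silence unlikely. That is also plausible. These are existing contacts that could carry reports, which is why the fix is cheap, but none is given that task.

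Finally, consent pages are not in the file and IRB reporting rules are not in the documents. Either may contain contact instructions or deadlines. The point therefore concerns the protocol text only.

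A reader might go further and infer that a serious event would wait a full month before the PI learned of it, or that the weakness belongs to home exercise alone. The documents support neither. The month would apply only if the summary were the sole route, which no section says. The silence on serious events covers on-site testing as well.

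**Conclusion.** The point holds as a gap in the monitoring plan: one monthly rule for all adverse events, no faster route for serious ones in any setting, and no stated method for collecting events at home although their number is a primary-aim measure. It is worth correcting before enrolment.

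Its size cannot be given. The documents contain no event rate and no actual delay, the serious risks are described as very rare, and only 20 physician-cleared participants are planned. The conclusion assumes that the removed consent pages and the IRB's rules do not already supply the missing instruction, and that coaching contains no adverse event question beyond its description. It does not bear on how the effect sizes are calculated. Nor do the documents support requiring physician re-clearance after every serious event, which a reader might think follows. The defect is about reporting and collection, and the decision afterwards already belongs to the investigator.

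**What to change.** Keep the monthly summary and amend II.I.2 in two respects.

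- **Serious events.** Staff, coaches and study partners report any serious event to the PI promptly on learning of it, for example within 24 hours (an assumed figure) or sooner if the IRB requires. The investigator then decides on pause or termination under II.F.3. The rule applies to home sessions and on-site testing alike.
- **Collection.** Coaches ask every participant one fixed adverse event question at each scheduled coaching session, starting in week 1. Serious and minor counts are shown separately.

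The cost is a short paragraph in the protocol, one question in contacts that already take place, and a brief explanation to coaches and study partners. The downsides are a small added reporting duty and more minor events recorded. Asking everyone the same question from the start, and separating the counts, keeps that rise from being mistaken for a safety problem.

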APPENDIX I: VULNERABLE POPULATIONS

- I. We have a consent form for surrogate decision maker. We also have assent. These are available in our informed consent materials.
- II. **Cognitively or decisionally impaired individuals:** We have a consent form for surrogate decision maker. This is available in our informed consent materials.
